12.1 Measurement

Entry evaluation includes demographic data, medical history, clinical presentation, physical findings, medications, laboratory data and echocardiographic examinations. The blood test needs to be handled by each center's SOP t, and the collected blood does not require storage after analysis. The blood specimen handling and which collected for the study is responsible for the centers participated in the study All the specimens gathered for the study will be handled by the Experienced sonographers will perform comprehensive two- dimensional and Doppler echocardiographic examinations, and the pre-randomization baseline echo will be read by clinical site echocardiography investigator to assess the degree of MR which will determine echocardiographic eligibility for participation in the trial. After this initial assessment, the study echo will be sent to the Echocardiography Core Lab for centralized reading by a blinded investigator. Eligibility is determined after a patient undergoes a thorough evaluation of clinical and echocardiographic data. After the patient has signed informed consent, the randomization procedures will take place.

Each subject enrolled in the trial will be assigned a study identification (ID) number so that study information will be confidential. The link between subject name and ID number will be stored only at the site where the subject receives clinical care.

12.1.1 Schedule of Measurements

Visit number	1	2	3	4	5
Time of Visit*	day 1	week 4	week 12	week 24	week 48
Inclusion/Exclusion criteria	X				
Information & Informed consent	X				
Physical examination	X	X			X
Echocardiography [‡]	X				X
Dispense study medication	X		X	X	
Laboratory test ^{†‡}	X	X			X
Adverse events		X	X	X	X

^{*} Time of visit: within +/- 7 days of the designated calendar day

NT-pro BNP, Urine analysis, chest PA and EKG

Visit 2: CBC, blood chemistry and electrolytes, urine analysis

12.2 Follow up: study patients will be follow up for 12 months after randomization

12.2.1 Clinical follow up

All subjects who participate in the study will be followed up in outpatient clinic on week 4, week 8, month 6 and month 12 after randomization. (All visits needs to be done within +/- 7 days of the designated calendar day). Investigator collects symptoms or clinical adverse events of the subjects and prescribes study drugs to them.

12.2.2 Echocardiographic follow up

Echocardiography will be performed on month 12(visit4) free of charge to all of the study patients.

12.2.3 Laboratory follow up

Laboratory tests include CBC, blood chemistry and urine analysis will be done on week 4(visit 1) and month 12(visit 4). Chest PA and EKG will be done on month 12(visit 4).

13 Risk benefit evaluation

13.1 Potential risk of the study participation

There are some risk or side effects that can be caused by study drug or for the consequence of blood sampling.

Clinical trials have proven the safety and tolerability of ertugliflozin. The side effects of ertugliflozin is described below;

^{**} Visit 1, visit 5: CBC, blood chemistry, electrolytes, lipid battery, BUN, HbA1C,

^{***}Echocardiography and laboratory tests can be performed either on the day of visit 0 or within 30 days from visit 0.

Genital mycosis, itching sense at the vagina, increased urine volume, thirsty, hypoglycemia, and weight loss at high doses. Even if it is very rare cases (0.1%), Ketoacidosis has been reported as a life threatening side effect. All the participants are required to be done the blood tests, echocardiography, and electrocardiogram at the beginning and the end of the trial period to evaluate the effects of treatment. The blood tests are performed in order to evaluate side effects of the study drug at the first month visit. Standard medical examinations are performed on every visit. Most significant discomfort which can be caused by participating in this study would be blood sampling. In rare cases, infection at the needle puncture site may occur. Blood collection is performed three times during the test. About 5 to 15 mL (1 to 3 teaspoons) of blood is taken depending on the type of laboratory test and it is required to monitor the safety and wellness of the subject. All collected samples are used only for the study purpose and are not stored and then discarded.

13.2 Potential benefit of the study participation

Up until now, there is no definitive drug treatment for functional mitral regurgitation, and furthermore, its effectiveness in surgical treatment is limited. On the other hand, ertugliflozin, a sodium-glucose co-transporter-2 (SGLT-2) inhibitor, is a drug that is expected to have a therapeutic effect on left ventricular remodeling by reducing the preload and afterload of the heart through natriuresis. It can be expected to have a superior effect in improving functional mitral regurgitation compared to conventional heart failure medication if ertugliflozin has a therapeutic effect on left ventricular remodeling in patients with functional mitral regurgitation accompanied by left ventricular dysfunction.

Even if the subjects belong to the placebo group (control group), they continue to take the angiotensin receptor blocker (ARB), the medication which is expected to weaken left ventricular dilatation and remodeling, and the other treatments recommended within standard treatment for heart failure (beta blockers, diuretics) Etc.). Moreover the study team continues follow-up observations, so it is thought that it will be more advantageous in terms of long-term prognosis. Furthermore, the results of this clinical trial will contribute to the development of medical research both domestically and internationally.

13.3 Result of benefit analysis

The potential risk of the study is very low, and immediate action is possible even if it appears. It is thought that the benefit of participating in the study sufficiently outweight the risk since this study is expected to improve the long-term prognosis associated with cardiovascular complications in both the test and active control groups.

14 Predictable side effect and caution

The safety and efficacy of ertugliflozin have been studied in many present clinical trials, which reported side effects such as genitourinary fungal infection (females: 9% to 12%; males: 4%), headache (3% to 4%), hypovolemia (2% to

4%), hypoglycemia (3%), increased thirst (1% to 3%), weight loss (2%), severe hypoglycemia (1%), increased urine output (2% to 3%), vulvovaginal pruritus (2% to 3%), back pain (3%), renal insufficiency (1% to 3%), nasopharyngitis (3%). Increased LDL cholesterol, increased serum phosphate, decreased eGFR, increased serum creatinine, acute renal failure, increased hemoglobin, ketoacidosis, pyelonephritis, urinary tract infection, urinary tract infection with sepsis has been reported rarely.

15 Withdraw criteria

All patients have the right to withdraw at any point during the study without prejudice. The investigator may discontinue any patient at any time if medically necessary. However, it will be documented whether or not each patient completed the clinical study. If the study treatment(s) or observations are discontinued in any patient, the reason will be recorded and the executive committee must be notified promptly. It is imperative to obtain complete follow-up data for all patients, whether or not they receive their assigned treatment. Every attempt should be made to collect follow-up information, except for those patients who specifically withdraw consent for release of such information. All procedures and laboratory specimens or tests requested for evaluation following the assigned treatment should be carried out when possible, whether or not a patient continues to receive treatment according to the protocol. Patients will not be replaced in this trial.

- 1) Withdrawal of informed consent
- 2) Acute adverse drug reaction (ex. allergy, hypersensitivity to the drug)
- 3) Unable to continue participation due to unexpected medical illness
- 4) Any severe suspected drug-related adverse event
- 5) Not satisfactory to the inclusion/exclusion criteria
- 6) Any unexpected medical treatments or interventions that were performed during the trial without notice to investigators and have any possibility to affect the result of the trial.
- 7) Poor compliance to the investigator's request.
- 8) Pregnancy

16 Study Endpoint and data acquisition and analysis

16.1 Endpoint

16.1.1 Primary Endpoint

Change of effective regurgitant orifice area (EROA) of functional mitral regurgitation from baseline to 12 months follow-up

16.1.2 Secondary Endpoint

- Change of regurgitant volume from baseline to 12 months follow-up
- Change of left ventricular end-systolic volume from baseline to 12 months follow-up
- Change of left ventricular end-diastolic volume from baseline to 12 months follow-up
- Change of NT-proBNP (N-terminal of the prohormone brain natriuretic peptide) from baseline to 12 months follow-up
- Change of left atrial volume index from baseline to 12 months follow-up
- Change of left ventricular global longitudinal strain from baseline to 12 months follow-up

16.2 Echocardiographic Evaluation

Echocardiographic evaluation will be performed at baseline and 12 months follow-up. Echocardiographic evaluation should have a minimum window period of 6 weeks after discharge in patients hospitalized due to heart failure. Experienced sonographers who are unaware of the patients' clinical characteristics and treatment assignments will perform comprehensive two-dimensional and Doppler echocardiographic examinations. End-systolic dimension, end-diastolic dimension, end-diastolic interventricular septal and posterior wall thickness of the LV will be measured from parasternal M-mode acquisitions. End-systolic volume, end-diastolic volume and EF of the LV will be obtained using the biplane Simpson method. Incomplete leaflet closure area will be measured on apical 4-chamber view. Regional wall motion abnormalities will be analyzed using a 16-segment model. The following protocol is required for estimation of effective regurgitant orifice area and regurgitant volume (12).

Protocol for PISA (proximal isovelocity surface area) method

- 1. Optimize color flow imaging of mitral regurgitation from an apical window.
- 2. Expand the image by the zoom mode.
- 3. Shift the color flow zero baseline in the direction of flow to increase hemispheric PISA; the aliasing velocity should be set between 0.2 and 0.4 m/s.
- 4. Select the most satisfactory hemispheric PISA at mid-systole.
- 5. Record 3-5 cycle clip of PISA as well as still frame of an ideal PISA.
- 6. Measure the radius of the PISA at mid-systole from a frame with an ideal PISA.
- Record a complete signal of the mitral regurgitation jet with continuous wave Doppler and capture a minimum of 3 consecutive cardiac cycles.
- 8. Measure the peak velocity and time-velocity-integral of the mitral regurgitation jet.

- 9. Determine EROA of the MR by dividing the regurgitant flow rate, calculated as $2\pi r^2 \times$ aliasing velocity, where r is the radius of PISA, by peak MR velocity.
- 10. Determine regurgitant volume by multiplying EROA by TVI of MR jet.

Echo study will be sent to the Echocardiography Core Lab for centralized analysis. The primary and secondary echocardiographic efficacy analyses will be done on off-line digital computerized review system by investigators who are blinded to treatment allocation and previous echocardiographic measures. Echocardiographic analyses will be done at baseline and 12 months.

16.3 Analysis of primary and secondary end point

All primary and secondary endpoints will be analyzed on an intention-to-treat basis (all patients analyzed as part of their assigned treatment group). For intention-to-treat analysis, all patients who sign the written informed consent form and are randomized in the study will be included in the analysis, regardless of whether or not they actually received the treatment to which they were assigned. The prespecified subgroups defined at baseline are ischemic versus nonischemic cause of functional MR, presence versus absence of DM, and sinus rhythm versus atrial fibrillation. The consistency of treatment effect will be assessed among prespecified subgroups with tests for interaction.

Baseline demographic and clinical variables will be summarized for each of the treatment groups. All continuous variables will be summarized as mean and SDs, or medians (with 95% confidence intervals [CIs]) as appropriate. Categorical variables will be summarized as frequencies and percentages and compared between treatment groups using chi-square test or Fisher's exact test.

The primary and secondary outcomes of this trial are the change of severity of functional MR and degree of left ventricular remodeling at 12 months after pharmacological treatment, assessed by EROA, regurgitant volume, LV end-systolic and end-diastolic volume and LV global longitudinal strain. The null hypothesis is that there is no difference in the EROA at 12 months after enrollment between patients treated with ertugliflozin compared to patients treated with placebo. The primary null hypothesis will be tested in an intention-to-treat analysis using a 0.05 level two-tailed t test if data are normally distributed, otherwise using the Mann-Whitney U test.

17 Participant Safety and Confidentiality

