9.3.2 Basis of calculation

We would like to have 90% power to detect a 0.05 cm² difference in EROA at 12 months between ertugliflozin and placebo group. Using a two-sided t-test with an alpha level of 0.05, sample size of 204 or 102 patients per treatment arm is required. In our previous trial (Kang DH, et al. Angiotensin receptor neprilysin inhibitor for functional mitral regurgitation, Circulation 2019;139:1354-1365), change in effective regurgitant orifice area was significantly greater in the ARNI group than the ARB group (-0.058 ± 0.095 versus -0.018 ± 0.105 cm2; P=0.032) and difference in change between the two groups was 0.040 ± 0.019 . Based on our previous trial, we assume that a common baseline mean value is 0.21 cm² and a common SD of the change from baseline is 0.11

cm² in both groups, and SD of the difference in change between the two groups is 0.019 cm². Assuming a dropout rate of 10%, the target number of patients to be randomized is 224.

COVID-19 pandemic seriously affected enrollment of study patients. Although the rate of patient recruitment was much lower than expected, the sponsor made a decision to adhere to the original study timeline and provide new study drug no longer in 2022. According to expiration date of supplied study drug, the Executive Committee decided to stop enrollment in December 2022 without knowledge of any trial data and the actual number of study patients was 128, smaller than the target sample size of 224 patients. Although the smaller actual sample size may result in an underpowered study to provide the hazard ratio, this trial is still expected to show significant differences in primary or secondary endpoints with careful assessment of outcomes and follow-up of all study patients.

10 Study timeline

On the basis of a lower than expected rate of patient recruitment and a limited supply of study drug, the Executive Committee finished enrollment in December 2022 without knowledge of any trial data. Overall study will require 38 months to complete, including 26 months of recruitment and 12 months of follow up and close out

- First patient in: November 2020
- Last patient in: December 2022
- Last patient out: December 2023
- First results available: March 2024

11 Trial Design

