22.4 Early Stopping Guideline

The IRB will be powered to recommend suspension of enrollment or termination of the study based on safety concerns. This study will not be stopped early based on efficacy results.

23 Publication Policy

No results will be released publicly before completion of the final analysis regarding the primary endpoint of this study. The statistical analysis will be performed according to the prespecified analysis plan as described in this protocol. The Executive Committee will review the primary outcome data according to the prespecified statistical analysis plan, and then will provide the data to the principal investigator which will in turn (a) first prepare a formal presentation to the Executive Committee members and (b) after taking under account the input and comments of the Executive Committee will proceed with submitting the manuscript .No study results will be released to the scientific or lay community without the approval of the Executive Committee. Authorship of the primary outcome paper will be credited collectively to the "Investigators."

24 Miscellaneous

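### Does section 16.3 need a written rule for patients who have no 12-month EROA?

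*Combined protocol and SAP*

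**What the plan says.** Section 16.3 states that, for intention to treat, "all patients who sign the written informed consent form and are randomized in the study will be included in the analysis". The same sentence goes on to say that this holds whatever treatment the patient actually received, and the sentence before it explains intention to treat as analysis within the assigned group. The primary null hypothesis is tested "using a 0.05 level two-tailed t test if data are normally distributed, otherwise using the Mann-Whitney U test".

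The outcome is observed once after baseline; section 16.2 says "Echocardiographic evaluation will be performed at baseline and 12 months follow-up". Section 23 points to no separate plan: "The statistical analysis will be performed according to the prespecified analysis plan as described in this protocol".

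Three other places bear on missing echoes:

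- Section 9.3.2 expects some loss. It says "sample size of 204 or 102 patients per treatment arm is required", and then "Assuming a dropout rate of 10%, the target number of patients to be randomized is 224". For the 128 actually enrolled, it counts on success "with careful assessment of outcomes and follow-up of all study patients".
- Section 15 calls complete follow-up imperative whether or not the patient received the assigned treatment, and excepts only those who withdraw consent to release of the information. It adds: "All procedures and laboratory specimens or tests requested for evaluation following the assigned treatment should be carried out when possible", whether or not treatment continues.
- Section 11.5 has each patient's evaluability decided and documented before treatment codes are broken. It lists no criteria.

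**The concern.** Read literally, the plan promises to include every randomised patient but names tests that need a 12-month value. With no intermediate echo, there is no later EROA to borrow from. A patient without the final echo must either leave the comparison or be given a value or rank, and the plan does not say which. It also names no sensitivity analysis and does not mention deaths.

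Two things would be at stake. The result could be described as covering all randomised patients when it does not. And if echoes are missing for reasons tied to both outcome and arm, such as death, heart-failure admission or withdrawal, the estimate could be biased. Blinded evaluability decisions prevent selection by arm but do not remove that bias. With 128 patients instead of 224 the trial has little power to spare, so a rule chosen late could matter.

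**Working it through.** **The plan's own figures (section 9.3.2).** Difference 0.05 cm², SD of change 0.11 cm², two-sided alpha 0.05, power 90%.

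- n per arm = 2 × [(1.960 + 1.282) × 0.11 / 0.05]² = 101.7, so 102 per arm and 204 in total. This matches the plan.
- Dropout: 204 × 1.10 = 224.4, the stated 224. Dividing by 0.90 gives 227, a difference of 3 patients. So 224 − 204 = 20 patients were not counted on for the test.

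**Number missing among 128.** No rate is given for the enrolled patients. Carrying over 10% is an assumption: 128 × 0.10 = 12.8, about 13 missing and 115 analysed (58 and 57). Power for 0.05 cm² is 73.0% with all 128 and 68.3% with 115 (normal approximation).

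**Available-case result if 0.05 cm² is observed.**

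- SE = 0.11 × √(1/58 + 1/57) = 0.0205
- t = 0.05 / 0.0205 = 2.44 on 113 df, p = 0.016
- Smallest significant difference = 0.0406

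**Stress test on the active arm only** (10% of that arm missing, available-case SE kept).

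- All missing active patients lose the full benefit: 0.05 − 0.10 × 0.05 = 0.045, p = 0.030.
- Shortfall that removes significance: (0.05 − 0.0406) / 0.10 = 0.094 cm². This is 0.85 SD, or 0.094 − 0.05 = 0.044 cm² worse than the placebo mean.

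| Assumed missing | Observed difference | Analysed | Tipping shortfall | p if full observed benefit lost |
|---|---|---|---|---|
| 5% | 0.05 | 122 | 0.211 (1.92 SD) | 0.019 |
| 10% | 0.05 | 115 | 0.094 (0.85 SD) | 0.030 |
| 15% | 0.05 | 109 | 0.055 (0.50 SD) | 0.046 |
| 10% | 0.045 | 115 | 0.044 (0.40 SD) | 0.051 |

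At an observed 0.040, the difference in the earlier trial cited in section 9.3.2, 115 patients give p = 0.054, so there is no significant result to overturn.

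**Bias when missingness depends on baseline EROA.** This was simulated with 64 per arm, a true difference of 0.050, about 10% missing per arm, a logistic slope of 1 per SD of baseline EROA, assumed baseline-change correlations of −0.3 and −0.5, and 6000 runs per setting.

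- Slope in one arm only: the available-case estimate is off by 0.003 and 0.005 cm², in either direction according to the arm. The larger figure is 0.005 / 0.0205 = 0.24 of the SE. Imputation from baseline brings it to 0.000.
- Same slope in both arms: bias 0.000.
- SD of the estimate: about 0.020 with or without imputation, so imputation gains no precision.

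**The case for a change.** The strongest case for a change is that the omission is definite, costs little to close, and can be closed credibly only before codes are broken. Intention to treat assigns a patient to an arm but supplies no missing value. Section 15 governs data collection and cannot produce an echo after death. The choice of rule also has consequences: setting missing patients to zero change in all 128, with 10% missing per arm, would cut the expected difference to 0.045 cm² and power to 63.8%, against 68.3% for available cases. And the result is not robust everywhere: an observed 0.045 cm² at 10% missing becomes p = 0.051 once the benefit in the missing active patients is removed.

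Much of this stands. No rule is written, and a report should state how many echoes and deaths there were in each arm and why echoes were missing. But it does not show that the planned analysis is wrong. A t test on change, run by assigned arm, has an obvious default: it uses patients who have the change. The dropout allowance is routine sizing and does not define an analysis set. The near-borderline cases arise because the observed effect lies close to the significance limit, and a written rule would not move it. Imputation from baseline corrects only missingness that baseline explains, where the error is already small. For the rest, a delta or worst-rank analysis is a reasonable option, but its form is a matter of preference.

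Echo timing is a separate matter. Section 16.2 asks for 6 weeks between heart-failure discharge and echo, while sections 12.1.1 and 12.2.1 allow visits 7 days either side, so a discharge in the last 42 − 7 = 35 days before the visit date cannot meet both. Those sections also differ on week 48 or month 12. That is a scheduling inconsistency, and no admission rate is given from which to count the patients affected. The 30-day footnote refers to Visit 0, which section 9.2 identifies as screening, so it does not bear on the final echo.

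**Conclusion.** No change to the plan follows. Section 16.3 leaves its missing-data policy unwritten, and analysts would fill it sensibly by comparing patients with a 12-month EROA in their assigned arms. Sections 15 and 11.5 limit how many echoes are lost and prevent selection with knowledge of the arm.

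At the assumed 10% missing, an observed 0.05 cm² stays significant after full loss of benefit in missing active patients (p = 0.030). This also holds at 5% and 15%. Baseline-related missingness shifts the estimate by at most 0.005 cm² in the settings simulated, and by nothing if it acts alike in both arms.

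This rests on the 10% rate set for 224 patients, an SD of 0.11 cm² and an observed effect near 0.05 cm². The true missing rate, and the bias from missingness that baseline does not predict, cannot be derived from the documents. A much higher loss, or clear imbalance between arms, would call for a sensitivity analysis in the report.

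### Section 16.3 leaves the primary test unadjusted in both branches although baseline EROA and the three stratification factors are collected; the test is valid but may give up power that a 128-patient trial needs

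*Combined protocol and SAP*

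**What the plan says.** Section 16.3 sets the primary test: "The primary null hypothesis will be tested in an intention-to-treat analysis using a 0.05 level two-tailed t test if data are normally distributed". For data that fail this condition there is a second branch, also without covariates: "otherwise using the Mann-Whitney U test". No covariate, ANCOVA or stratified test is named anywhere in the document.

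The material for adjustment is already collected. Sections 12.1.1 and 16.2 provide for echocardiography at baseline and at 12 months. Section 11.1 stratifies randomization by ischemic or non-ischemic cause, diabetes and cardiac rhythm. In the analysis these factors return only as subgroups: "The consistency of treatment effect will be assessed among prespecified subgroups with tests for interaction".

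The endpoint in 16.1.1 is "Change of effective regurgitant orifice area (EROA) of functional mitral regurgitation from baseline to 12 months follow-up". The null hypothesis in 16.3 is worded differently: "The null hypothesis is that there is no difference in the EROA at 12 months after enrollment". Section 9.3.2 sizes the trial on a "difference in EROA at 12 months between ertugliflozin and placebo group" but uses the SD of change, assuming "a common baseline mean value is 0.21 cm² and a common SD of the change from baseline is 0.11" cm².

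Section 9.3.2 also discloses that "the actual number of study patients was 128, smaller than the target sample size of 224 patients", and accepts that the trial may be underpowered.

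**The concern.** Subtracting baseline fixes the slope of 12-month EROA on baseline EROA at 1. If the true slope is lower, as regression to the mean would produce, the change score carries avoidable noise. ANCOVA estimates the slope instead. Leaving stratification factors out of the model also makes the test somewhat conservative if those factors predict the outcome.

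In a fully recruited trial this might be left alone. Here enrollment closed at 128 of 224, so power can no longer come from more patients. Adjusting for values already in the database is one of the few ways left to gain precision.

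**Working it through.** **Inputs from 9.3.2:** difference 0.05 cm², SD of change 0.11 cm², two-sided alpha 0.05, 102 per arm for 90% power, 10% dropout, 128 actual patients (taken as 64 per arm under the 1:1 allocation in 11.1). **Assumed, because the documents do not give them:** correlation rho between baseline and 12-month EROA, 0.3 to 0.9; ratio k of the 12-month SD to the baseline SD, 1 to 1.25.

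**Step 1, the plan's own figure.** n per arm = 2 × (1.960 + 1.282)² × (0.11/0.05)² = 101.7, so 102. This matches. Noncentral-t power at 102 per arm is 89.8%.

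**Step 2, the planned t test at the actual size.** The noncentrality is 0.05 / (0.11 × √(2/64)) = 2.571 on 126 df, which gives 72.3% power. With 10% dropout, 128 × 0.9 = 115.2, or 57.6 per arm, power is 67.7%.

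**Step 3, ANCOVA with four covariates** (baseline EROA and three factors).
- Baseline SD implied by the SD of change: s0 = 0.11 / √(1 + k² − 2·rho·k).
- Residual SD = k × s0 × √(1 − rho²).
- Charge for estimating four covariates: variance × (1 + 4/(N − 7)), with N − 6 df.

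Example with N = 128, k = 1, rho = 0.5: s0 = 0.110, residual SD = 0.0953, multiplier 1 + 4/121 = 1.033. The noncentrality is 0.05 / (0.0953 × √(2/64) × √1.033) = 2.92 on 122 df, which gives 82.6%.

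| rho | k = 1, N = 128 | k = 1.25, N = 128 | k = 1, N = 115 | k = 1.25, N = 115 |
|---|---|---|---|---|
| 0.3 | 87.6% | 80.9% | 83.8% | 76.4% |
| 0.5 | 82.6% | 75.7% | 78.3% | 71.0% |
| 0.7 | 77.7% | 71.7% | 73.1% | 66.9% |
| 0.8 | 75.4% | 70.9% | 70.6% | 66.1% |
| 0.9 | 73.1% | 73.1% | 68.3% | 68.3% |

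Against 72.3% and 67.7%, the change runs from -1.4 to +15.3 points with 128 and from -1.6 to +16.1 with 115. The loss is largest where the slope rho × k equals 1 (0.8 × 1.25), because subtraction is then already the best use of baseline.

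**Step 4, is the loss overstated?** The charge in step 3 treats all four covariates as imbalanced by chance. If stratification balances the three factors, only baseline EROA is charged, with multiplier 1 + 1/(N − 4) = 1 + 1/124. The worst loss with 128 then falls from 1.4 to about 0.4 points.

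**Step 5, non-normal data (simulations that have not been independently verified).** With assumed log-normal errors (sigma 0.8) and an assumed Shapiro-Wilk gate, the planned two-branch rule had 86-99% power. ANCOVA alone had 73-88%, up to 26 points lower. A rule that also adjusts the rank branch had 98-99%. Simulated size of the adjusted rule was 0.042-0.058. These figures serve only as a reason not to drop the rank branch.

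**The case against.** The strongest reply is that nothing here is an error. The t test on change matches the sizing, baseline is already partly used, the tests hold their level, and the shortfall is disclosed. That stands: this is a choice between valid analyses.

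The second reply is that the gain is not a property of the plan. This also stands. The documents give no baseline SD or correlation. At rho 0.7 to 0.9 with 128 analysed, the change is only about -1.4 to +5 points; gains of ten points or more in the grid need rho of about 0.5 or less with k = 1. There are reasons to expect a slope below 1: entry requires an ERO above 0.10 cm² (9.1), EROA depends on a squared radius (16.2), and core-lab readers are blinded to previous measurements (16.2). These make a gain plausible but do not establish it.

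Third, the remedy keeps a data-driven choice of test, and it does not settle how a missing 12-month EROA is handled. Both remarks are fair.

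A reader might also infer that the null hypothesis commits the trial to comparing raw 12-month values. The documents do not support that. The sentence before it in 16.3, the abstract, Figure 1 in 11.2 and section 16.1.1 all speak of change. The wording needs tidying, as does the unnamed normality check, but neither is a separate fault.

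**Conclusion.** The point holds as a matter of efficiency. Both branches of the primary test ignore covariates that are already collected, in a trial whose planned t test has 72% power with 128 analysed (68% with 115) for the plan's own difference and SD. Under the assumed rho of 0.3-0.9 and k of 1-1.25, ANCOVA gives 71-88% with 128 and 66-84% with 115. The benefit may be substantial or close to nothing, and the worst case in this range is a loss of about 1.5 points.

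Two stronger readings should be resisted. One is that the unadjusted test is biased or inflates type I error: ignoring prognostic strata makes it, if anything, conservative. The other is that adjustment would restore the planned 90%: no setting in the grid reaches that, and the documents do not provide the correlation on which any forecast depends. A change to the analysis is worth making; confidence in the size of the gain is only moderate.

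**What to change.** In 16.3, state the null hypothesis as no difference between groups in change in EROA from baseline to 12 months. Test it at two-sided 0.05 by ANCOVA of change in EROA on treatment, baseline core-lab EROA, cause, diabetes and rhythm, and report the adjusted difference in cm² with its 95% CI. In this model the treatment effect is the same whether the outcome is change or 12-month EROA.

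Keep a non-normal branch adjusted for the same covariates (rank ANCOVA). Fix the normality check before unblinding, for example Shapiro-Wilk at 0.05 on pooled residuals from the model without treatment. Keep the unadjusted t test and Mann-Whitney test on change as sensitivity analyses. In 9.3.2, word the target as a difference in change in EROA.

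**Cost.** No new data or patients are needed. Up to about 1.5 points of power are lost if the slope is near 1 and the strata are not prognostic. In the rank branch the p value and the cm² interval come from different methods and can disagree.

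**Timing.** Section 24.2 requires a written, IRB-approved amendment. It should precede database lock and be written by people without unblinded data, since 24.7 lets the DMC analyse efficacy. Section 10 gives last patient out as December 2023 and first results as March 2024; the documents do not say whether the database is locked. If it is, report the adjusted analysis as a labelled sensitivity analysis.
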